**Table 3: Schedule for correlative blood sample collections**

| Timepoint                   | Correlative blood samples  |
|-----------------------------|--|
| Pre-Treatment Cycle 1 Day 1 | 5 purple top tubes (50 ml total)
2 ACD tubes (17 ml total)
1 PAXgene tube (8.5 ml total)   |
| Pre-Treatment Cycle 2 Day 1 | 2 purple top tube (20 ml total)
2 ACD tubes (17 ml total)
1 PAXgene tube (8.5 ml total)    |
| Pre-Treatment Cycle 3 Day 1 | 2 purple top tubes (20 ml total)
5 ACD tubes (42.5 ml total)
1 PAXgene tube (8.5 ml total) |
| Pre-Treatment Cycle 6 Day 1 | 2 purple top tubes (20 ml total)
5 ACD tubes (42.5 ml total)
1 PAXgene tube (8.5 ml total) |
| Time of progression         | 5 purple top tubes (50 ml total)
2 ACD tubes (17 ml total)
1 PAXgene tube (8.5 ml total)   |

## 8. BIOSPECIMEN STUDIES AND PROCEDURES

Tumor tissue, peripheral blood, and possibly normal urothelium will be used for biospecimen-based research in this study. Full details of specimen collection and processing can be found in the CLM.

Correlative studies may include genomic sequencing of tumor tissue and/or peripheral blood and immune monitoring studies including T cell receptor sequencing and flow cytometry and/or mass cytometry on tissue and/or peripheral blood, antigen-specific T cell assays, HLA typing, and gene expression.

### 8.1 Tissue

Analysis of tumor tissue will include assessment for changes in the composition of immune cells, tumor cells, and tumor microenvironment. Immune cell composition and changes in the tumor microenvironment will be analyzed by platforms including but not limited to immunohistochemistry, flow cytometry, and mass cytometry. Tumor cells will be analyzed by immunohistochemistry, DNA, and RNA sequencing. Normal tissue or blood will be used for the germline genome. An effort will be made to identify tumor antigens for each subject using strategies including, but not limited to, collating the “antigenome” using immunohistochemistry data as well as identifying mutation-derived tumor antigens through genome sequencing and computational biology approaches to predict epitope: MHC binding affinity. Subject HLA typing will be done by sequence specific oligonucleotide probing and sequence specific priming of genomic DNA using standard procedures. T-cell responses will be detected using standard ELISPOT and intracellular cytokine assays or other emerging technologies. Tumor tissue will also be utilized for PD-L1 expression as determined by immunohistochemistry.

### **8.1.1 Archival Tissue**

Representative formalin-fixed paraffin-embedded (FFPE) tumor specimens in paraffin blocks (blocks preferred) or at least 15 unstained slides will be identified prior to subject registration and shipped after registration but prior to C1D1. Representative formalin-fixed paraffin-embedded (FFPE) tumor specimens in paraffin blocks (blocks preferred) or at least 15 unstained slides. If archival tissue is not available and the subject is undergoing a standard of care biopsy, tissue from the biopsy is required to be submitted for correlative analyses. Subjects without adequate baseline tumor tissue may be considered for enrollment on a case by case basis after discussion with the sponsor-investigator. Specimens will be utilized for cellular and molecular analyses including but not limited to DNA sequencing, RNA sequencing, and tissue imaging/multiplex staining.

### **8.1.2 Tissue collected during routine clinical procedures**

Surplus tissue remaining after routine standard of care procedures (e.g., metastatic biopsies) will be collected during this study. Subjects may have tumor tissue obtained during the course of the study or at the time of disease progression for clinical purposes (e.g., confirmation of disease progression, management of complication of disease progression, etc.). Specimens obtained in these settings may be accessed by the research team to facilitate an understanding of the pharmacodynamic effects of treatment at the level of the tumor and microenvironment including mechanisms of treatment resistance. Subjects will have the option of whether samples obtained during standard of care procedures may be used for research purposes.

## **8.2 Blood Samples**

For blood samples, the volume of blood and type of tube to be used for each collection is specified in Table 3 and CLM. Collection of whole blood samples is mandatory for participation in this study. Blood samples for research will also be collected for subjects receiving re-treatment after progression.

### **8.2.1 Blood for Immune cell subsets**

The quantity and composition of immune cells in the peripheral blood will be analyzed by flow cytometry or mass cytometry. Antigen specific T cell responses will be detected as described above.

### **8.2.2 Peripheral blood for DNA and RNA**

Plasma will be stored for future ctDNA isolation and quantitative expression using sequence specific primers and/or for exome sequencing. DNA from whole blood may be used to germline sequencing to facilitate analysis of somatic tumor DNA sequencing. Whole blood will be stored for gene expression profiling from RNA.

## **8.3 Stool for microbiome analysis**

Prior to treatment, patients will provide a stool sample from a single bowel movement for microbiome analysis as per the CLM. Stool samples will be analyzed to assess microbiome diversity and composition. Exploratory analyses correlating clinical outcomes and diversity/composition as well as assessment of metabolomics and metagenomic whole genome sequencing may be performed. Stool samples will not be collected during re-treatment with tremelimumab.

#### **8.4 Storage of Biospecimens**

Excess biospecimens not completely utilized in these experiments will be stored indefinitely at HCRN for future use in research focused on GU malignant diseases that are yet to be determined. All specimens collected will maintain the assigned sequence ID number of the corresponding patient. Deidentified samples may be shared with other research institutions. We believe that allowing for storage and usage of the remaining samples for future research is ethically justified and a preferred option to discarding these materials given the potential impact on improving clinical outcomes for subjects with bladder cancer. Subjects will be given the option to store excess specimens during the informed consent process.

#### **8.5 Confidentiality of Biospecimens**

Samples that are collected will be identified by a subject's sequence ID assigned at the time of registration to the trial. Any material issued to collaborating researchers will be anonymized and only identified by the subject's sequence ID.

### **9. CRITERIA FOR DISEASE EVALUATION**

See section 5.1.3 and 5.1.4 for criteria for continuing treatment past RECIST 1.1 disease progression.

#### **9.1 RECIST 1.1**

##### **9.1.1 Measurable disease**

The presence of at least one measurable lesion. If the measurable disease is restricted to a solitary lesion, its neoplastic nature should be confirmed by cytology/histology.

###### **9.1.1.1 Measurable lesions**

Measurable lesions are defined as those that can be accurately measured in at least one dimension (longest diameter to be recorded) as  $\geq 20$  mm by chest x-ray, as  $\geq 10$  mm with CT scan, or  $\geq 10$  mm with calipers by clinical exam. All tumor measurements must be recorded in millimeters (or decimal fractions of centimeters).

###### **9.1.1.2 Non- Measurable lesions**

All other lesions (or sites of disease), including small lesions (longest diameter  $<10$  mm or pathological lymph nodes with  $\geq 10$  to  $<15$  mm short axis), are considered non-measurable disease. Bone lesions, leptomeningeal disease, ascites, pleural/pericardial effusions, lymphangitis cutis/pulmonitis, inflammatory breast disease, and abdominal masses (not followed by CT or MRI), are considered as non-measurable.

**NOTE:** Cystic lesions that meet the criteria for radiographically defined simple cysts should not be considered as malignant lesions (neither measurable nor non-measurable) since they are, by definition, simple cysts.

‘Cystic lesions’ thought to represent cystic metastases can be considered as measurable lesions, if they meet the definition of measurability described above. However, if non-cystic lesions are present in the same subject, these are preferred for selection as target lesions.

### 9.1.1.3 Malignant lymph nodes

To be considered pathologically enlarged and measurable, a lymph node must be  $\geq 15$  mm in short axis when assessed by CT scan (CT scan slice thickness recommended to be no greater than 5 mm). At baseline and in follow-up, only the short axis will be measured and followed.

### 9.1.1.4 Baseline documentation of “Target” and “Non-Target” lesions

#### Target lesions

All measurable lesions up to a maximum of 2 lesions per organ and 5 lesions in total, representative of all involved organs, should be identified as **target lesions** and recorded and measured at baseline. Target lesions should be selected on the basis of their size (lesions with the longest diameter), be representative of all involved organs, but in addition should be those that lend themselves to reproducible repeated measurements. It may be the case that, on occasion, the largest lesion does not lend itself to reproducible measurement in which circumstance the next largest lesion which can be measured reproducibly should be selected. A sum of the diameters (longest for non-nodal lesions, short axis for nodal lesions) for all target lesions will be calculated and reported as the baseline sum diameters. If lymph nodes are to be included in the sum, then only the short axis is added into the sum. The baseline sum diameters will be used as reference to further characterize any objective tumor regression in the measurable dimension of the disease.

#### Non-target lesions

All other lesions (or sites of disease) including any measurable lesions over and above the 5 target lesions should be identified as **non-target lesions** and should also be recorded at baseline. Measurements of these lesions are not required, but the presence, absence, or in rare cases unequivocal progression of each should be noted throughout follow-up.

## 9.2 Response Criteria

### Evaluation of target lesions

|                          |  |
|--------------------------|--|
| Complete Response (CR)   | Disappearance of all target lesions. Any pathological lymph nodes (whether target or non-target) must have reduction in short axis to $<10$ mm.  |
| Partial Response (PR)    | At least a 30% decrease in the sum of the diameters of target lesions, taking as reference the baseline sum diameters  |
| Progressive Disease (PD) | At least a 20% increase in the sum of the diameters of target lesions, taking as reference the smallest sum on study (this includes the baseline sum if that is the smallest on study). In addition to the relative increase of 20%, the sum must also demonstrate an absolute increase of at least 5 mm. (Note: the appearance of one or more new lesions is also considered progressions). |
| Stable Disease (SD)      | Neither sufficient shrinkage to qualify for PR nor sufficient increase to qualify for PD, taking as reference the smallest sum diameters while on study.   |

### Evaluation of non-target lesions

|                          |  |
|--------------------------|--|
| Complete Response (CR)   | Disappearance of all non-target lesions and normalization of tumor marker level. All lymph nodes must be non-pathological in size (<10 mm short axis)

NOTE: If tumor markers are initially above the upper normal limit, they must normalize for a subject to be considered in complete clinical response. |
| Non-CR/ Non-PD           | Persistence of one or more non-target lesion(s) and/or maintenance of tumor marker level above the normal limits   |
| Progressive Disease (PD) | Appearance of one or more new lesions and/or unequivocal progression of existing non-target lesions. Unequivocal progression should not normally trump target lesion status. It must be representative of overall disease status change, not a single lesion increase.   |

\*Although a clear progression of “non target” lesions only is exceptional, in such circumstances, the opinion of the site physician should prevail.

### 9.3 Evaluation of best overall response

The best overall response is the best response recorded from the start of the treatment until disease progression/recurrence (taking as reference for PD the smallest measurements recorded since the treatment started). In general, the subject's best response assignment will depend on the achievement of both measurement and confirmation criteria.

| Target Lesions | Non-Target lesion             | New Lesion | Overall response |
|----------------|-------------------------------|------------|------------------|
| CR             | CR                            | No         | CR               |
| CR             | Non-CR/ Non-PD                | No         | PR               |
|                | Not evaluated                 | No         | PR               |
| PR             | Non-CR/ Non-PD/ not evaluated | No         | PR               |
| SD             | Non-CR/ Non-PD/ not evaluated | No         | SD               |
| PD             | Any                           | Yes or No  | PD               |
| Any            | PD*                           | Yes or No  | PD               |
| Any            | Any                           | Yes        | PD               |

\*In exceptional circumstances, unequivocal progression in non-target lesions may be accepted as disease progression.

Subjects with a global deterioration of health status requiring discontinuation of treatment without objective evidence of disease progression at that time should be classified as having “symptomatic deterioration”. Every effort should be made to document the objective progression even after discontinuation of treatment. In some circumstances it may be difficult to

distinguish residual disease from normal tissue. When the evaluation of complete response depends on this determination, it is recommended that the residual lesion be investigated (fine needle aspirate/biopsy) to confirm the complete response status.

## **9.4 Definitions for Response Evaluation – RECIST 1.1**

### **9.4.1 First documentation of response**

The time between initiation of therapy and first documentation of PR or CR.

### **9.4.2 Confirmation of Response**

To be assigned a status of complete or partial response, changes in tumor measurements must be confirmed by repeat assessments performed no less than four weeks after the criteria for response are first met.

### **9.4.3 Duration of Response**

Duration of overall response—the period measured from the time that measurement criteria are met for complete or partial response (whichever status is recorded first) until the date that recurrent or progressive disease is objectively documented, taking as reference the smallest measurements recorded since treatment started.

### **9.4.4 Duration of Overall Complete Response**

The period measured from the time that measurement criteria are met for complete response until the first date that recurrent disease is objectively documented.

### **9.4.5 Objective response rate**

The objective response rate is the proportion of all subjects with confirmed PR or CR according to RECIST, from the start of treatment until disease progression/recurrence (taking as reference for progressive disease the smallest measurements recorded since the start of treatment).

### **9.4.6 Progression Free Survival**

A measurement from the start of the treatment until the criteria for disease progression is met or death occurs, taking as reference the smallest measurements recorded since the treatment started.

Progression free survival will be measured from the date of initial treatment to the earliest date of disease progression, resection of measurable tumor or death for subjects who fail; and to the date of last contact for subjects who remain at risk for failure.

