#### 2.2.2 Secondary Endpoints

- Safety will be determined according to the NCI Common Terminology Criteria for Adverse Events (NCI CTCAE) v4.03
- The disease control rate is the rate of objective response and stable disease as determined by RECIST 1.1
- Duration of response will be the time from the first documentation of response to the time of progression
- Progression-free survival which is defined as the time from treatment initiation to death or progression, depending on which occurs first
- Overall survival is defined as the time from treatment initiation to death

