#### 12.2.2 Definition of Secondary Endpoints

- Safety will be determined according to the NCI Common Terminology Criteria for Adverse Events (NCI CTCAE) v4.03
- Duration of response will be the time from the first documentation of response to the time of progression as per RECIST 1.1 or death
- Progression-free survival which is defined as the time from treatment initiation to death or progression, depending on which occurs first
- Overall survival is defined as the time from treatment initiation to death

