### 12.6.2 Analysis Plans for Secondary Objectives

Any subject who receives at least one dose of treatment on this protocol is evaluable for toxicity. Toxicity rates will be summarized using frequency tables. Disease control rates will be analyzed based on the exact binomial test. Duration of response will be the time from the first documentation of response to the time of progression or death will be summarized using frequency tables. Progression free survival and overall survival curves will be based on the Kaplan-Meier method.

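### PFS is censored at last contact while phone-only follow-up is possible before progression; PFS and DoR event sets differ between sections; the DoR tables have no rule for ongoing responses

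*Combined protocol and SAP*

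**What the plan says.** **PFS censoring.** The second paragraph of Section 9.4.6 measures PFS "to the date of last contact for subjects who remain at risk for failure". Section 12.6.2 names Kaplan-Meier for PFS and overall survival, but Section 12 sets no censoring date, so 9.4.6 stands alone.

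**Follow-up.** Section 7, footnote 8, requires scans about every 2 months in Cycles 1-7 and every 3 months afterwards, until progression. Footnote 15 has progression-free subjects followed 3-monthly for progression. Section 6.4 and footnote 15 both offer 3-monthly phone follow-up to subjects who decline to return to the site.

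**PFS events.** The first paragraph of 9.4.6 runs "until the criteria for disease progression is met or death occurs". The second runs to the "earliest date of disease progression, resection of measurable tumor or death for subjects who fail". Section 12.2.2 reads: "Progression-free survival which is defined as the time from treatment initiation to death or progression, depending on which occurs first". Section 2.2.2 has the same event set as 12.2.2.

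**DoR events.** Section 2.2.2: "Duration of response will be the time from the first documentation of response to the time of progression". Section 9.4.3: "until the date that recurrent or progressive disease is objectively documented". Section 12.2.2: "to the time of progression as per RECIST 1.1 or death".

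**DoR analysis.** Section 12.6.2 takes DoR "to the time of progression or death will be summarized using frequency tables". It does not extend Kaplan-Meier to DoR.

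**The concern.** A phone call cannot establish RECIST progression. If a subject stops scans before progression but stays reachable, last-contact censoring credits the unimaged months as progression-free and pushes the PFS curve up.

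The conflicting event sets allow two analysts, each following a different section, to report different PFS or DoR from the same data.

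DoR is a censored duration, and a frequency table cannot show it properly unless the plan says how a continuing response is displayed. Continuing responses are likely. In the earlier tremelimumab monotherapy study described in Section 1.2.2, median DoR was not estimable and all 6 confirmed responders had disease control at 12 months. Section 12.1 relies on durability to argue that even a low response proportion could matter, so DoR should be readable without guesswork.

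**Working it through.** **1. Event sets side by side**

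| Section | PFS ends at | DoR ends at |
|---|---|---|
| 2.2.2 | progression or death | progression |
| 9.4.3 | – | recurrence or progression |
| 9.4.6, first paragraph | progression or death | – |
| 9.4.6, second paragraph | progression, resection or death | – |
| 12.2.2 | progression or death | progression or death |
| 12.6.2 | not restated | progression or death |

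One resection before progression would be 1/28 = 3.6 percentage points of PFS at most. Expected responders at the design alternative are 0.15 × 28 = 4.2, so one death without documented progression concerns about a quarter of them.

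**2. Size of the last-contact effect**

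The plan states no figure to reproduce. From the documents: 28 subjects, 12-month accrual, 24-month study duration, and scans at about 2, 4 and 6 months and then every 3 months. Assumed: exponential PFS with median 3 months; median survival after progression 6 months; a fraction *f* = 10% to 20% who stop imaging, equally often after 0, 1 or 2 scans (*s* = 0, 2 or 4 months); phone contact to cut-off; deaths known. Every subject has at least 12 months of potential follow-up, so the 6-month estimate under last-contact censoring is a simple proportion.

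- Full imaging: 0.5^(6/3) = 0.250.
- A subject who stops at *s* counts as event-free at 6 months if not progressed by *s* and alive at 6 months. With these medians the probability is 0.25 + 0.5^(*s*/6) − 0.5, that is 0.750, 0.544 and 0.380 for *s* = 0, 2 and 4. The mean is 0.558.
- *f* = 10%: 0.9 × 0.25 + 0.1 × 0.558 = 0.281.
- *f* = 20%: 0.8 × 0.25 + 0.2 × 0.558 = 0.312.

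The largest shift is 0.062, or 0.062 × 28 = 1.7 subjects. The standard error is √(0.25 × 0.75/28) = 0.082. At 12 months the 20% case reads about 12% against 6%. That is about 6 points, against a standard error of √(0.0625 × 0.9375/28) = 0.046.

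Simulation (400,000 subjects per scenario) agrees with these figures and shows the dependence on contact time. With 20% stopping, 6-month PFS reads 25.0% if contact ends 1 month after the last scan, 27.8% at 3 months and 31.1% at 6 months.

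**3. Median PFS**

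With a true median of 2.5 to 3.5 months the observed median stays at the 4-month scan. With a true median of 2 months, the first scan falls exactly where the curve reaches 50%. Last-contact censoring at 20% then moves the median from about 2 to about 3.4 to 3.8 months, depending on simulation details. The effect depends on the true median and the scan grid.

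**4. What the alternatives achieve** (contact to cut-off, true 6-month PFS 25%)

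| Rule | 10% stop | 20% stop |
|---|---|---|
| Last contact | 28.2% | 31.2% |
| Last scan, all deaths kept | 27.0% | 29.0% |
| Last scan, deaths after two or more missed scans also censored | 24.9% | 24.6% |

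Last-scan censoring with all deaths kept leaves about 2 to 4 points of upward bias: subjects off imaging who die count as event-free until death. In the 20% case the third rule sets aside 7.6% of subjects' deaths, 0.076 × 28 = 2.1.

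**5. Ongoing responses**

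Assume exponential DoR, response documented at 2 months, and the same accrual and cut-off. Then 17%, 40% or 55% of responses are ongoing at the 24-month cut-off for true medians of 6, 12 or 18 months. Of 4.2 responders that is 0.7, 1.7 or 2.3.

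**The case against.** The strongest reply is that phone contact is only a means of survival follow-up. In Section 6.4 the phone sentence follows the statement that all subjects are followed for survival. In footnote 15 it follows the sentence on survival follow-up after progression. Subjects who have progressed already have a PFS event. For the rest, footnote 8 requires scans until progression, and Section 9.3 asks for efforts to document progression after stopping for symptomatic deterioration. Section 6.5 asks for assessments to be completed when a subject leaves the protocol. This stands in large part and makes the gap narrow. It does not close it: neither phone sentence is limited to progressed subjects, and a scan requirement does not help for a subject who declines visits.

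It is also fair that Sections 12.2.2 and 12.6.2 agree on DoR, that resection is probably rare because Sections 3.2 and 5.2.2 exclude target lesions from permitted local treatment, and that DoR in about 4 responders can be described by a table or listing. The event-set conflicts are therefore matters of harmonisation. What remains for DoR is the missing rule for ongoing responses.

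A reader might infer that PFS is seriously inflated. The documents give no phone-only rate, so they do not support that. The opposite inference, that median PFS is safe, is not general either (step 3). A reader might also infer that ongoing responses will be counted as completed or dropped; the plan states neither.

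**Conclusion.** The concern holds as a limited defect in how secondary endpoints are defined. The only PFS censoring rule can count unimaged time as progression-free. Under assumed rates of 10% to 20% stopping imaging with contact to cut-off and a true median of 3 months, 6-month PFS is overstated by about 3 to 6 points, below one standard error with 28 subjects. There is no material shift if contact and imaging stop together. The stopping rate, contact time and survival after progression are all assumptions.

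The resection conflict within 9.4.6, the two DoR end points and the missing display rule for ongoing responses follow from the text alone and need no assumption. None of this reaches the primary response-rate test, the stopping rules or the sample size. The change is worth making, at modest priority.

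**What to change.** 1. In 9.4.6 and 12.2.2, censor event-free subjects at the last evaluable tumor assessment, or at first dose if there is no post-baseline assessment.
2. Use one PFS event set, progression or death, in 2.2.2, 9.4.6 and 12.2.2, and delete resection as an event from 9.4.6.
3. Use one DoR definition, first documented response to progression or death, in 2.2.2, 9.4.3, 12.2.2 and 12.6.2, with the same censoring.
4. Report DoR by Kaplan-Meier, with the number ongoing and a listing of each responder's duration and status.
5. Add a PFS sensitivity analysis that censors, at the last evaluable assessment, deaths occurring after two or more consecutive missed scheduled scans. It addresses the 2 to 4 points left by item 1.

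**Cost.** Wording in five subsections and minor programming; scan dates are already collected. PFS may read slightly shorter, and Kaplan-Meier on about 4 responders is imprecise, hence the listing. These rules still assume that stopping imaging is unrelated to progression. If 20% skip the very scan that would have shown it, 6-month PFS reads about 35% with last-contact censoring, 34% with item 1 and 30% with item 5, against 25%. The report should therefore state how many subjects stopped imaging before progression.
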